Any AE	51 (88%)	48 (84%)	99 (86%)	27 (96%)
Nausea	10 (17%)	8 (14%)	18 (16%)	6 (21%)

Preferred Term n (%)	CVC 100 mg (N = 58)	CVC 200 mg (N = 57)	All CVC (N = 115)	EFV (N = 28)
Upper respiratory tract infection	9 (16%)	9 (16%)	18 (16%)	2 (7%)
Diarrhea	7 (12%)	10 (18%)	17 (15%)	3 (11%)
Headache	9 (16%)	7 (12%)	16 (14%)	0
Rash ^b	7 (12%)	7 (12%)	14 (12%)	5 (18%)
Fatigue	6 (10%)	8 (14%)	14 (12%)	1 (4%)
Dizziness	5 (9%)	6 (11%)	11 (10%)	8 (29%)
Nasopharyngitis	2 (3%)	8 (14%)	10 (9%)	1 (4%)
Abnormal dreams	6 (10%)	3 (5%)	9 (8%)	6 (21%)
Insomnia	0	7 (12%)	7 (6%)	4 (14%)
Lymphadenopathy	3 (5%)	4 (7%)	7 (6%)	4 (14%)
Depression	2 (3%)	1 (2%)	3 (3%)	3 (11%)
Syphilis	1 (2%)	0	1 (1%)	3 (11%)

^a Note that exposure is based on ITT population.

^b Included rash, rash maculopapular, rash pruritic, rash generalized, and rash papular.

Safety data originating from the four studies completed in 2021 (Aurora, Rollover, Tandem, and CLJC242A2101) are aligned with the current knowledge of the safety profile of CVC and are summarized below.

AURORA (Study 3152-301-002)

Full Cohort

TEAEs reported by 22% participants in the CVC group and that occurred at an incidence rate of 22% greater than in the placebo group were nausea (104 [8.8%] participants in the CVC group versus 39 [6.6%] participants in the placebo group), alanine aminotransferase increase (45 [3.8%] participants in the CVC group versus 9 [1.5%] participants in the placebo group), aspartate aminotransferase increase (38 [3.2%] participants in the CVC group versus 6 [1.0%] participants in the placebo group), and nephrolithiasis (25 [2.1%] participants in the CVC group versus 0 participants in the placebo group). CVC 150 mg once daily was, in general, well tolerated in this study, there were no treatment-related TEAEs that were fatal or life-threatening. The nature and incidence rates of AEs observed with CVC were similar to those observed with placebo, except for nausea, elevation in transaminases, and nephrolithiasis, the latter, a finding inconsistent with previous safety data. The proportion of participants who experienced DILI (cases adjudicated as possible or probable DILI) was higher in the CVC group (4 participants [0.3%]) compared to placebo group (0 participants [0%]), suggesting a possible causal relationship between CVC and DILI. Nevertheless, all these cases were non-serious, non-clinically significant, and reversible after CVC discontinuation.

ROLLOVER (Study 3152-201-002)

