The FDG-PET/CT imaging will be associated with radiation exposure of ~ 19 to 21 milliSieverts (mSv). This exposure is similar amount of radiation that a person is exposed to when undergoing a single exercise stress test with myocardial perfusion imaging (~ 15 mSv for technetium studies, and ~ 21 to 24 mSv for thallium studies), and is substantially below the 50 mSv limit that is established by Institutional Review Boards (IRBs) in the United States (the annual limit established for radiation workers). To further limit the radiation risks to participants, anyone who reports any significant radiation exposure over the course of the year prior to study entry (defined in the exclusion criteria) or who has a history of radiation therapy will be excluded. There may be rare instances when imaging has to be repeated because the initial image obtained was deemed uninterpretable. If this occurs, the exposure may approach 28 to 32 mSv.

Biomarkers

As CVC binds and inhibits function of CCR2 and CCR5, interference with binding and clearance of CCL2 and MIP-1a, MIP-1b, and RANTES (CCR5 ligands) might be anticipated. As we hypothesize that monocyte/macrophage activation may be attenuated by CVC administration, we also plan to monitor levels of sCD14 and sCD163, indices of monocyte/macrophage activation.

Supporting Pharmacokinetic Data from Allergan/AbbVie

In Study 104, there was a 2.39-fold increase in CVC Cmax, a 3.55-fold increase in CVC AUC from time 0 to 24 hours post dose (AUC0-24), and a 5.24-fold increase in CVC Cmin with RTV co-administration.

In Study 105, there was no evidence of a drug-drug interaction on CVC by tenofovir disoproxil fumarate (TDF); however, co-administration with CVC increased plasma TDF exposure by approximately 28%-36%.

In Study 107, there was a 2.17-fold increase in CVC Cmax, a 3.13-fold increase in CVC AUC0-24, and a 4.17-fold increase in Cmin with DRV/r co-administration, which is comparable to the effect seen with co-administration of RTV alone in Study 104. In Study 113, there was no meaningful effect of CVC on plasma darunavir (DRV) or RTV exposure.

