7.2 Adverse Event Collection Requirements for this Protocol

All AEs must be recorded on the eCRFs if any of the following criteria have been met.

- All new Grade ≥ 2 diagnoses and the following targeted events regardless of grade:
 - AIDS-defining conditions (refer to the CDC HIV Classification and the WHO Staging System for HIV Infection and Disease)
 - Bone fractures (verbal history accepted)
 - Coronary heart disease
 - Cancer (exclusive of basal/squamous cell skin cancer)
 - Diabetes
 - Tuberculosis, active or latent
 - Hepatitis C virus infection
 - Hepatitis B virus infection
 - SARS-CoV-2 infection
 - Any infection
- All Grade ≥ 3 signs and symptoms, except fever and chills, which should be reported regardless of grade
- All Grade ≥ 2 laboratory findings
 - NOTE: Creatinine and eGFR should be graded using the categorical mL/min values from the DAIDS AE Grading Table. The percent change criteria from baseline will not apply to A5415.
- Any Grade ≥ 3 AE that occurs due to or during the FDG-PET/CT imaging
- All AEs that led to a change in study treatment regardless of grade
- All AEs meeting SAE definition or EAE reporting requirement

NOTE: SAEs or events meeting EAE reporting requirements should also be entered into the DAIDS Adverse Experience Reporting System (DAERS), an Internet-based reporting system.

All AEs that are reported must have their severity graded. To grade AEs, sites must refer to the Division of AIDS Table for Grading the Severity of Adult and Pediatric Adverse Events (DAIDS AE Grading Table), corrected Version 2.1, July 2017, which can be

found on the DAIDS RSC Web site: <https://rsc.niaid.nih.gov/clinical-research-sites/daids-adverse-event-grading-tables>.

Serious Adverse Events (SAEs)

An SAE is defined as any untoward medical occurrence that:

- Results in death
- Is life-threatening
- Requires inpatient hospitalization or prolongation of existing hospitalization
- Result in persistent or significant disability/incapacity
- Is a congenital anomaly/birth defect
- Is an important medical event that may not be immediately life threatening or result in death or hospitalization but may jeopardize the participant or may require intervention to prevent one of the other outcomes listed in the definition above.

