11.4 Anticipated Outcomes

Average trough estimates for CVC and each ART will be calculated for comparisons outlined above. Trough estimates for CVC at weeks 4, 8, 12, and 24 will be time adjusted to provide a composite exposure estimate as described above.

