APPENDIX I: RESULTS OF CENICRIVIROC MESYLATE (CVC) STUDIES

Appendix I Table 1

Study Number/Phase	Study Title	Participant Description	Dose & Administration	CVC Formulation	Endpoints
Allergan Study 652-1-104 Phase 1	A phase 1 multiple-dose, cross-over study to assess the potential interaction between TBR-652 and RTV in healthy volunteers	20 healthy adults	50 mg CVC po × 10 days, then 50 mg CVC + 100 mg RTV po × 10 days (CVC administered as 2×25 mg tablets after a standardized meal) [Standardized meal contained approximately 500-700 kcal and <15-20 g fat]	DP3_25 formulation, manufactured by Emerson Resources	1. Plasma PK of CVC with/without RTV 2. Safety, tolerability
Noteworthy Findings:					
RTV significantly increased exposure to CVC (based on ratios of LS geometric means: 2.39-fold increase in Cmax and a 3.55-fold increase in AUC0-24) and reduced exposure to CVC metabolites. There were no clinically important safety findings.					
Allergan Study 652-1-105 Phase 1	A phase 1, open-label, single-dose, randomized, cross-over study to assess the potential interaction between TDF and TBR-652 in healthy volunteers	21 healthy adults	150 mg CVC po, 300 mg TDF, 150 mg CVC po + 300 mg TDF (CVC administered as 6×25 mg tablets after a standardized breakfast) [Standardized breakfast contained approximately 500-700 kcal and <15-20 g fat] 14-day washout between regimens	DP3_25 formulation, manufactured by Emerson Resources	1. Plasma PK of CVC with/without TDF 2. Plasma PK of TDF with/without CVC 3. Safety, tolerability
Noteworthy Findings:					
TDF had no effect on CVC exposure. Co-administration of CVC and TDF did not affect the AUC0-t and AUC0-∞ of TDF, based on the protocol-defined equivalence range of 0.70-1.43. However, co-administration with CVC increased the AUC and Cmax of TDF by approximately 28%-36%, with the 90% CI for the Cmax of TDF falling outside the 0.80-1.25 “no effect” range. There were no clinically important safety findings.					

Study Number/Phase	Study Title	Participant Description	Dose & Administration	CVC Formulation	Endpoints

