3152-301-002 Phase 3	AURORA: A Phase 3, Multicenter, Randomized, Double-Blind, Placebo-Controlled Study to Evaluate the Efficacy and Safety of Cenicriviroc for the Treatment of Liver Fibrosis in Adult Subjects with Nonalcoholic Steatohepatitis	
Part 1: A total of 1288 participants with NASH were analyzed in Part 1 (859 participants in Arm A; and 429 participants in Arm B) [1293 participants were randomized (861 to the CVC group and 432 to the placebo group)]
 
Part 2: A total of 1769 participants with NASH were analyzed in the full study cohort (1180 participants in Arm A, and 589 participants in Arm B) [A total of 1778 participants were enrolled in the full study cohort. Of these, 1185 participants were randomized to the CVC group and 593 participants were randomized to the placebo group.]
	Cenicriviroc mesylate 150 mg immediate release oral tablet (Arm A) or placebo (Arm B) once daily (2:1)	Cenicriviroc mesylate 150 mg immediate release oral tablet (Arm A) or placebo (Arm B) once daily (2:1)	
Part 1: Proportion of participants with improvement in fibrosis by at least 1 stage (NASH CRN system) AND no worsening of steatohepatitis (no worsening of lobular inflammation or hepatocellular ballooning grade) Safety and tolerability
 
Part 2: Composite endpoint of histopathologic progression to cirrhosis (defined by NASH CRN Fibrosis Stage 4), liver-related clinical outcomes, and all-cause mortality, as measured by the time to first occurrence of any of the listed adjudicated events (clinical outcomes composite endpoint) Safety and tolerability

Study Number/Phase	Study Title	Participant Description	Dose & Administration	CVC Formulation	Endpoints

Noteworthy findings: The primary endpoint was not met for Part 1, leading to early termination of the study. No meaningful numerical or statistical difference was observed between CVC 150 mg once daily and placebo with respect to the key efficacy endpoints regarding liver histology at Month 12 relative to the screening biopsy in adult participants with a liver biopsy diagnosis of NASH and Stage 2 or 3 liver fibrosis (by NASH CRN system). CVC 150 mg once daily was, in general, well tolerated in this study, and there were no treatment-related AEs that were fatal or life-threatening.
					

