6.1 Adverse Events

Analysis set(s): Safety set

Statistics: N (%)

Listing: Public ID, AE start day, AE term, Grade, Action taken with treatment, Relationship to treatment.

- 1) Table of all new, post-entry AEs by MedDRA PT grouped by SOC (reported in ClinicalTrials.gov)
- 2) Listing of longitudinal creatinine and eGFR with creatinine-related AEs
- 3) Table/listing of SAEs by MedDRA PT grouped by SOC, excluding those related to PET/CT
- 4) Listing of all AEs related to study treatment by MedDRA PT grouped by SOC, excluding those related to PET/CT
- 5) Table/listing of all AEs related to PET/CT scan by MedDRA PT grouped by SOC

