9.1.2 Change in ART Trough Estimates

Analysis set(s): Complete case set
Grouped by: Specific ART Bictegravir, Dolutegravir, Rilpivirine
Stratification: None
Analysis method: paired t-test of pre-study treatment and participant-level average post-study treatment ART trough estimates with null hypothesis of no difference between pre- and post- study measures.

Table	Columns for each group: Pre, Post, Change	
Characteristic	Pre-, Post- Treatment Statistic(s)	Change Statistic
Average <DRUG> trough concentration	Mean (st.dev.), Median (Q1, Q3), and P10, P90	Mean, 95% confidence interval, p-value

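### After baseline the SAP only lists eGFR and creatinine, so a mean decline on CVC that stays within one grading category would appear in no by-arm output

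*Protocol*

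**What the plan says.** **Background.** Protocol 2.1 (Supporting Pharmacokinetic Data) says that "co-administration with CVC increased plasma TDF exposure by approximately 28%-36" per cent. Appendix I describes the study (652-1-105) as single-dose, in 21 healthy adults, and adds: "Co-administration of CVC and TDF did not affect the AUC0-t and AUC0-∞ of TDF, based on the protocol-defined equivalence range of 0.70-1.43". It also notes that the 90% CI for the TDF Cmax fell outside 0.80-1.25. For AURORA, which used the same 150 mg dose, Protocol 2.1 reports "nephrolithiasis (25 [2.1%] participants in the CVC group versus 0 participants in the placebo group").

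**Data collected.** Protocol 6.1 schedules blood chemistries and eGFR at screening, entry and weeks 4, 12 and 24. Section 6.3.5 requires post-entry creatinine and eGFR to be recorded whatever the grade. Section 8.2.2 names TDF in its guidance on reduced GFR.

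**Grading.** Protocol 7.2 collects laboratory findings as adverse events from Grade 2 upward. For creatinine and eGFR it says: "The percent change criteria from baseline will not apply to A5415".

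**Analysis.** SAP 5.5 summarises baseline eGFR by arm. SAP 6.1 tabulates new post-entry adverse events by preferred term, and the note under SAP 5.4 makes that table by arm. For the later renal values it plans a "Listing of longitudinal creatinine and eGFR with creatinine-related AEs". Neither eGFR nor creatinine is an outcome measure in SAP 3.3.

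**ART troughs.** Protocol 11.4 says: "Average trough estimates for CVC and each ART will be calculated for comparisons outlined above". SAP 9.1.2 has "Grouped by: Specific ART Bictegravir, Dolutegravir, Rilpivirine".

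**The concern.** Secondary Objective 1.3.3 is the safety of CVC in people on ART. Among ART drugs allowed in this trial, tenofovir is the one whose exposure the protocol reports as raised by CVC: atazanavir was also raised, but protease inhibitors are excluded, and efavirenz and dolutegravir were not meaningfully affected. The protocol collects the renal data needed to look for a consequence.

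The planned outputs would show individual participants with graded creatinine or eGFR events, and a listing of values. They would not show whether the average eGFR moved differently on CVC and on placebo. A reader of the report could not tell no difference from a difference that was never summarised.

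**Working it through.** **1. Can a mean decline reach any by-arm output?**

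- *AE table (SAP 6.1, item 1).* It counts recorded events. A creatinine or eGFR value becomes a recorded laboratory event only at Grade 2 or higher on the absolute categories (Protocol 7.2). The cut-offs are in an external grading table that the documents do not reproduce. Whatever they are, a fall that crosses none of them adds no graded laboratory event.
- *Listing (SAP 6.1, item 2).* It shows individual values and gives no arm-level mean, difference or interval.
- *Regression of change (SAP 7.2.3, extended by SAP 8).* It covers the change outcomes of SAP 3.3. eGFR and creatinine are not among them.
- *Baseline table (SAP 5.5).* Baseline only.

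So the values are held at four time points (entry and weeks 4, 12 and 24), and no planned output estimates the change by arm.

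**2. How precise would an estimate be?**

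Inputs: 110 enrolled (SAP 2.1), allocation 2:1, two-sided alpha 0.05 (SAP 4.2). The achieved split is not given, so 73 + 37 is assumed. The documents give no SD for eGFR change, so 8 to 12 mL/min/1.73 m2 is assumed.

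Check of the method on the plan's own figure: the two-sample t calculation with 50 + 25, difference 0.046 and SD 0.065 gives 81%, against the 80% stated in Protocol 10.4.

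Detectable difference at 80% power ≈ (t + 0.845) × √(1/n1 + 1/n2) in SD units; 95% CI half-width = t × the same root, where t is the two-sided 5% point on n1 + n2 − 2 degrees of freedom.

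- 73 + 37: root = √(0.01370 + 0.02703) = 0.2018. Detectable: (1.982 + 0.845) × 0.2018 = 0.57 SD. Half-width: 1.982 × 0.2018 = 0.40 SD.
- 62 + 31, about 15% loss (the rate Protocol 10.4 uses for non-imaging outcomes): root = 0.2200. Detectable: (1.986 + 0.845) × 0.2200 = 0.62 SD. Half-width: 1.986 × 0.2200 = 0.44 SD.

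| Assumed SD | 73 + 37: 80% power | 73 + 37: half-width | 62 + 31: 80% power |
|---|---|---|---|
| 8 | 4.6 | 3.2 | 5.0 |
| 10 | 5.7 | 4.0 | 6.2 |
| 12 | 6.8 | 4.8 | 7.5 |

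**3. Would a nephrolithiasis comparison help?**

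Reproducing the AURORA rate with the Appendix I denominators ("1180 participants in Arm A, and 589 participants in Arm B"): 25/1180 = 2.12%, matching the stated 2.1%. Fisher's exact test against 0/589 gives p = 0.00005 in that trial. At the same rate here, 73 × 0.0212 = 1.5 events are expected on CVC, and the chance of at least one is 1 − (1 − 0.0212)^73 = 79%. Significance would need at least 8/73 versus 0/37; power is about 0.02%. AURORA's follow-up time is not stated, so the 24-week rate could be lower.

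**4. Would tenofovir troughs help?**

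SAP 9 names the drugs with at least 10 users. TAF is on the list and TDF is not, so TDF has fewer than 10. With at most 9 TDF users (6 + 3 assumed), a between-arm comparison has 8% to 47% power for a 1.28- to 1.36-fold ratio, at assumed CVs of 60% down to 20%. The documents give no CVC-TAF data.

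**The case against.** The strongest reply is that renal safety is already covered. Nephrolithiasis recorded as a Grade 2 or higher diagnosis, as serious, or as leading to a treatment change appears by preferred term and arm, as do Grade 2 or higher creatinine and eGFR findings. This stands. A reader might infer that the listing is the only renal output; it is not.

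A reader might also infer that renal effects were singled out for no between-arm test. The documents do not support that: Protocol 10.6.3 and SAP 6 treat all safety descriptively and name no test.

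Nor do they establish that CVC harms the kidney through tenofovir. The 28-36% rise is from single doses in healthy adults with AUC read as equivalent, it concerns TDF rather than TAF, and no passage links nephrolithiasis to tenofovir. Protocol 2.1 itself calls the AURORA stones inconsistent with earlier safety data.

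Finally, it is tempting to say the SAP wrongly dropped tenofovir from the troughs. But FTC and 3TC also reach 10 users and are also absent, SAP 2.3.3 and SAP 9 mark the choice of drugs as pending, and SAP 9 limits PK to the CVC arm, so adding tenofovir would give no between-arm answer.

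None of this supplies an arm-level estimate of eGFR change. That gap remains.

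**Conclusion.** The concern holds in a narrow form. The later eGFR and creatinine values are collected in full but only listed, and with percent-change grading off the by-arm AE table cannot show a mean shift within a grading category. A by-arm estimate would have a 95% CI half-width of about 0.40 SD and 80% power for about 0.57 SD (4.6 to 6.8 mL/min/1.73 m2 at an assumed SD of 8 to 12), or about 0.62 SD with 15% loss. These figures rest on an assumed 73:37 split and assumed SDs, and the documents give no expected CVC effect on eGFR to set them against.

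The gap affects how fully Objective 1.3.3 is answered. It does not touch the primary outcome or any outcome measure listed in SAP 3.3. A separate nephrolithiasis analysis is not warranted at this sample size.

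**What to change.** In SAP 6.1, add one Safety-set table by arm of change in eGFR and creatinine from entry to weeks 4, 12 and 24, using the SAP 4.1.3 windows, with the between-arm difference and 95% CI. Show it overall, and descriptively (no test) for participants on tenofovir-containing regimens. State whether values after stopping study treatment are included. Keep the listing as support. No separate nephrolithiasis count is needed, since the AE table largely covers it.

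Cost: one extra table from data already on the eCRF, and one more comparison without multiplicity adjustment, which should be labelled as a safety estimate.

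Optional: when the pending ART selection for SAP 9.1.2 is settled, consider tenofovir in TAF users. This may need an added assay on samples already drawn. If it is not assayed, the report should say that Objective 1.4.7b does not address tenofovir.

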3.0 STUDY DESIGN

This is a double-blind, placebo-controlled phase II clinical trial comparing the intervention of CVC versus placebo for a duration of 24 weeks on arterial inflammation evaluated by FDG-PET/CT imaging. Image analysis will be performed by imaging specialists at the

central imaging core laboratory at the Massachusetts General Hospital (MGH) Imaging Trials Center (MITC). The imaging specialists at the core laboratory are blinded to the clinical history and treatment group classification of the participant.

A total of 93 participants will be randomized 2:1 to the CVC arm (Arm A) or placebo for CVC arm (Arm B). Stratification by statin use at randomization will ensure even distribution of statin use between the treatment groups.

Blood samples will be collected per the SOE.

4.0 SELECTION AND ENROLLMENT OF PARTICIPANTS

4.1 Inclusion Criteria

4.1.1 HIV-1 infection, documented by:

- Any licensed rapid HIV test or HIV enzyme or chemiluminescence immunoassay (E/CIA) test kit at any time prior to study entry AND
- Confirmed by one of the following:
- A licensed Western blot
- A second antibody test by a method other than the initial rapid HIV and/or E/CIA
- HIV-1 antigen, plasma HIV-1 RNA viral load, or
- Two HIV-1 RNA >1,000 copies/mL.

NOTE: The term “licensed” refers to a US FDA-approved kit, which is required for all IND studies, or for sites located in countries other than the United States, a kit that has been certified or licensed by an oversight body within that country and validated internally. Non-US sites are encouraged to use US FDA-approved methods for IND studies.

WHO (World Health Organization) and CDC (Centers for Disease Control and Prevention) guidelines mandate that confirmation of the initial test result must use a test that is different from the one used for the initial assessment. A reactive initial rapid test should be confirmed by either another type of rapid assay or an E/CIA that is based on a different antigen preparation and/or different test principle (e.g., indirect versus competitive), or a Western blot or a plasma HIV-1 RNA viral load.

4.1.2 Currently on a stable, continuous NNRTI-based or unboosted INSTI-based ART regimen for ≥ 48 weeks prior to study entry with no ART interruption longer than 7 consecutive days and with no plans to change ART during the course of the study.

NOTE A: Stable is defined as no within-class changes in ART regimen within 12 weeks prior to study entry and no between-class changes for 24 weeks prior to study entry.

NOTE B: Unboosted ART is defined as an ART regimen that does not include the pharmacologic booster COBI or RTV.

NOTE C: Modifications of ART formulation within 12 weeks prior to study entry (e.g., from standard formulation to fixed-dose combination of the same drugs), are permitted.

- 4.1.3 Screening HIV-1 RNA level below the limit of quantification (e.g., <20, <40, <50, or <75 copies/mL, depending on the assay) using an FDA-approved assay with a quantification limit of 75 copies/mL or lower performed by any US laboratory that has a Clinical Laboratory Improvement Amendments (CLIA) certification or its equivalent, or at any network-approved non-US laboratory that operates in accordance with Good Clinical Laboratory Practices (GCLP) and participates in appropriate external quality assurance programs within 90 days prior to study entry.
- 4.1.4 All HIV-1 RNA levels within 48 weeks prior to study entry below the limit of quantification (e.g., <20, <40, <50, or <75 copies/mL, depending on the assay) using an FDA-approved assay with a quantification limit of 75 copies/mL or lower performed by any US laboratory that has a CLIA certification or its equivalent, or at any network-approved non-US laboratory that operates in accordance with GCLP and participates in appropriate external quality assurance programs.

NOTE A: Up to two HIV-1 RNA determinations that are between the assay quantification limit and 500 copies/mL (i.e., “blips”) are allowed as long as the preceding and subsequent determinations are below the level of quantification.

NOTE B: The screening value may serve as the subsequent undetectable value following a blip.

- 4.1.5 CD4+ cell count >200 cells/mm³ obtained within 90 days prior to study entry at any US laboratory that has a CLIA certification or its equivalent, or at any network-approved non-US laboratory that is IQA certified.
- 4.1.6 At least one of the following cardiovascular risk factors (current diagnosis or receiving treatment, except where a time period is specified):
 - Clinical atherosclerotic disease (symptomatic atherosclerotic lesions in any vessel)
 - Subclinical atherosclerotic disease (coronary artery calcification [CAC] >10 or presence of non-obstructive plaques)
 - DM or prediabetes (hemoglobin A1c [HbA1c] ≥5.7%) or impaired fasting glucose (documented fasting glucose of >100 mg/dL within 6 months prior to study entry) or insulin resistance (HOMA-IR ≥2.6) or any one of these

- laboratory values within 6 months prior to study entry
- Obesity (body mass index [BMI] $\geq 30 \text{ kg/m}^2$) or enlarged iliac waist circumference (>40 inches in males, >35 inches in females)

NOTE A: BMI calculator is available at the Data Management Center (DMC) website: <https://www.fstrf.org/ACTG/ccc.html>.

- History of hypertension or blood pressure $\geq 130/80 \text{ mmHg}$ measured during screening
NOTE: See the A5415 Manual of Procedures (MOPS) for **blood pressure measurement guidance**.
- Elevated LDL cholesterol (fasting LDL of $>160 \text{ mg/dL}$; result from sample taken within 90 days prior to study entry can be used)
- Low HDL cholesterol ($<40 \text{ mg/dL}$; result from sample taken within 90 days prior to study entry can be used)
- Smoking (any current tobacco smoking)
- Family history of premature CAD (first degree relative with CAD prior to age 55 for male relative and 65 for female relative; participant report is acceptable)
- hsCRP $>2.0 \text{ mg/L}$ within 90 days prior to study entry without an active infection or acute illness at the time the sample was obtained

4.1.7 The following laboratory values obtained within 90 days prior to study entry by any US laboratory that has a CLIA certification or its equivalent, or at any network-approved non-US laboratory that operates in accordance with Good Clinical Laboratory Practices (GCLP) and participates in appropriate external quality assurance programs.

- Absolute neutrophil count (ANC) $>750/\text{mm}^3$
- Platelet count $>100,000/\text{mm}^3$
- Aspartate aminotransferase (AST) (SGOT) $\leq 5x$ upper limit of normal (ULN)
- Alanine aminotransferase (ALT) (SGPT) $\leq 5x$ ULN
- Alkaline phosphatase $\leq 5x$ ULN
- Estimated glomerular filtration rate (GFR) $\geq 60 \text{ mL/min}/1.73 \text{ m}^2$ as calculated using the Chronic Kidney Disease Epidemiology Collaboration (CKD-Epi) equation

NOTE: See the A5415 MOPS for further information and a link to the CKD-Epi equation and calculator.

4.1.8 Pre-entry FDG-PET/CT imaging (within 60 days prior to study entry) that has been deemed:

- Interpretable as assessed by the central imaging core laboratory
AND
- Without incidental findings that will preclude participation in the study at the discretion of the site investigator

4.1.9 No plans to receive immunizations 7 days prior to the week 24 study visit.

4.1.10 For study candidates of child-bearing potential, negative serum or urine pregnancy test within 90 days prior to study entry and prior to starting study treatment at study entry by any clinic or laboratory that has a CLIA certification or its equivalent, or is using a point of care (POC)/CLIA-waived test, or at any network-approved non-US laboratory or clinic that operates in accordance with Good Clinical Laboratory Practices (GCLP) and participates in appropriate external quality assurance programs.

NOTE: Reproductive potential is defined as individuals who have reached menarche and individuals who have not been post-menopausal for at least 12 consecutive months with follicle-stimulating hormone (FSH) ≥ 40 IU/mL or 24 consecutive months if an FSH is not available, or have not undergone surgical sterilization (e.g., hysterectomy, bilateral oophorectomy, tubal ligation or salpingectomy).

4.1.11 If participating in sexual activity that could lead to pregnancy, willingness of person of childbearing potential to use two forms of contraception while receiving study medication and for 3 months after stopping study medication as required.

NOTE A: Acceptable forms of contraception include:

- Barrier methods (condoms [male or female] with or without a spermicidal agent, diaphragm, or cervical cap [with spermicide])
- Hormone-based contraception (oral, patch, parenteral, implants, or vaginal ring)
- Intrauterine device (IUD)

NOTE B: If the participant is not of reproductive potential (individuals who are post-menopausal as defined above, or individuals who have undergone surgical sterilization [e.g., hysterectomy, bilateral oophorectomy, tubal ligation or salpingectomy]), they are eligible without requiring the use of a contraceptive method. Acceptable documentation of surgical sterilization and menopause is by participant-reported history.

4.1.12 Individuals ≥ 45 years of age.

4.1.13 Ability and willingness of participant or legal guardian/representative to provide informed consent.

